8.11.2 Treatment Period

The estimated duration of lenvatinib treatment is 1 year. However, participants receiving clinical benefit from lenvatinib treatment can continue treatment with lenvatinib until a treatment discontinuation criterion is met.

8.11.3 Telephone Contact or Visit

A telephone contact or visit will be scheduled to report BP and record AEs. Blood pressure can be taken, for example, at home or at a local pharmacy, and will be reviewed with the investigator or medically qualified designee (consistent with local requirements) on C1D8 to assess participants for development of early toxicity, as outlined in the SoA (Section 1.3). An unscheduled visit can occur prior to C1D15 if deemed necessary for safety by the investigator.

8.11.4 Participants Discontinued From Study Intervention but Continuing to be Monitored in the Study

The EOT visit will take place at the time lenvatinib is discontinued for any reason.

If the EOT visit takes place approximately 30 days from the last dose of lenvatinib, a separate Safety Follow-up visit is not required. All procedures required at the EOT and at the Safety Follow-up visit will be performed as a single visit.

8.11.5 Post-treatment Visits

8.11.5.1 Safety Follow-up Visit

The mandatory Safety Follow-up Visit should be conducted approximately 30 days after the last dose of study intervention or before the initiation of a new anticancer treatment, whichever comes first.

8.11.5.2 Efficacy Follow-up Visits

Participants who discontinue lenvatinib for a reason other than disease progression and/or initiation of new anticancer therapy will move into the Efficacy Follow-up Phase and will be assessed as outlined in the SoA (Section 1.3) to monitor disease status. Every effort should be made to collect information regarding disease status until the start of new anticancer therapy, disease progression, death, end of study, whichever occurs first. Information regarding poststudy anticancer treatment will be collected if new treatment is initiated. Participants who completed all efficacy assessments and/or will not have further efficacy assessments must enter the Survival Follow-up Phase.

8.11.5.3 Survival Follow-up Assessments

Participants will be offered survival follow-up for at least 1 year. Participant survival follow-up status will be assessed approximately every 12 weeks until death, withdrawal of consent, or the end of the study, whichever occurs first.

The first survival follow-up assessment should be scheduled as described below:

- For participants who discontinue treatment intervention and who will not enter the efficacy follow-up phase, the first survival follow-up assessment will be scheduled 12 weeks after the discontinuation visit and/or safety follow-up visit (whichever is last).
- For participants who completed assessments in the efficacy follow-up phase, the first survival follow-up assessment will be scheduled 12 weeks after the last efficacy assessment follow-up visit has been performed.

8.11.6 Survival Status

To ensure current and complete survival data is available at the time of database locks, updated survival status may be requested during the course of the study by the Sponsor. Upon Sponsor notification, all participants who do not/will not have a scheduled study visit or study contact during the Sponsor defined time period will be contacted for their survival status (excluding participants that have a previously recorded death event in the collection tool).

9 STATISTICAL ANALYSIS PLAN

This section outlines the statistical analysis strategy and procedures for the study. If, after the study has begun, changes are made to primary and/or key secondary hypotheses, or the statistical methods related to those hypotheses, then the protocol will be amended (consistent with ICH Guideline E9). Changes to exploratory or other non-confirmatory analyses made after the protocol has been finalized, along with an explanation as to when and why they occurred, will be documented in an sSAP and referenced in the CSR for the study. Post hoc exploratory analyses will be clearly identified in the CSR. A separate molecular profiling analysis plan will be developed to explicitly address exploratory biomarker objectives.

9.1 Statistical Analysis Plan Summary

Key elements of the SAP are summarized below; the comprehensive plan is provided in Sections 9.1-9.12.

Study Design Overview	An Open-Label, Multicenter Phase 2 Basket Study to Evaluate the antitumor activity and Safety of Lenvatinib in Children, Adolescents, and Young Adults with Relapsed or Refractory Solid Malignancies
Treatment Assignment	
A minimum of 36 evaluable participants will be enrolled: 9 evaluable participants in each of the tumor types. The final sample size of participants will depend on the number of tumor types that meet the futility bar and the antitumor activity in evaluable participants observed in the corresponding tumor cohort in Study E7080-A001-216. The enrollment in the HGG, RMS, and EWS/pPNET cohorts is capped at a maximum of 17 evaluable participants each. The enrollment for each tumor type expanded based on response in the other solid tumors' cohort is also capped at a maximum of 17 evaluable participants. Based on these factors and the projected enrollment period, it is estimated that up to approximately 150 participants could be enrolled.
 
The participants will receive lenvatinib 14 mg/m² orally once daily (equivalent to 24 mg QD, the adult daily dose).

Analysis Populations	
Antitumor activity: Evaluable Analysis Set (EAS), defined as all evaluable participants, who have measurable disease present at baseline and at least 1 postbaseline efficacy assessment, unless they have discontinued prior to the first efficacy assessment due to progressive disease.
 
Safety: Safety Analysis Set, defined as all participants who received at least 1 dose of the study drug.
 
Pharmacokinetic (PK): PK Analysis Set, defined as participants in Safety Analysis Set who had at least 1 measurable postdose plasma concentration with an adequately documented dosing history.

Primary Endpoint(s)	
The Primary Endpoint will be assessed for each tumor type: ORR, defined as the proportion of participants with a confirmed (≥ 4 weeks after initial response) CR or PR per RECIST 1.1 or RANO for HGG as assessed by investigator, at Week 16.

Key Secondary Endpoints	
 • ORR • BOR • DOR • DCR • CBR • PFS per RECIST 1.1 or RANO for HGG • AEs, SAEs, clinical laboratory values, vital signs, 12-lead ECGs, urine dipstick, Lansky play scores or Karnofsky performance status scores, physical examination findings, dental examination findings, height, and closure of proximal tibial plates. • Palatability questionnaire using a facial hedonic scale.

Statistical Methods for Key Efficacy Analyses	To evaluate for efficacy of lenvatinib, data on antitumor activity will be analyzed by each tumor type. Objective responses will count only confirmed CR and PR at Week 16. Estimated ORR and its exact 95% CI using the method of Clopper and Pearson will be presented. The ORR, DCR, and CBR will be provided with exact 95% CIs using the method of Clopper and Pearson, and the DOR will be analyzed for responders using Kaplan-Meier approach. PFS will be analyzed using Kaplan-Meier product-limit estimates. The cumulative PFS probabilities will be plotted over time as appropriate.
Statistical Methods for Key Safety Analyses	The incidence of treatment-emergent adverse events (TEAEs) and SAEs will be summarized by system organ class and preferred term. Continuous measures such as changes from baseline in laboratory test data, vital signs, 12-lead ECGs, cardiac function by echocardiography or MUGA scan, urine dipstick, and Lansky play scores or KPS scores will be summarized using descriptive statistics (mean, standard deviation, etc.) for baseline, on-treatment, and change-from-baseline values.
Interim Analyses	Multiple interim analyses may be performed in this study due to the sequential monitoring procedure. Results will be reviewed by the study team. Within each tumor type, the study will enroll a minimum of 9 evaluable participants.
Multiplicity	No additional multiplicity adjustment is required for this study.
Sample Size and Power	CCI

9.2 Responsibility for Analyses/In-house Blinding

The statistical analysis of the data obtained from this study will be the responsibility of the Clinical Biostatistics department of the Sponsor.

This study is being conducted as an open-label study (ie, participants, investigators, and Sponsor personnel will be aware of participant treatment assignments after each participant is enrolled and treatment is assigned).

The Clinical Biostatistics department will generate the allocation schedule(s) for study treatment assignment. Allocation will be implemented in an IVRS. Participants will be allocated by nonrandom assignment.

9.3 Hypotheses/Estimation

Objectives and hypotheses of the study are stated in Section 3.

9.4 Analysis Endpoints

Efficacy and safety endpoints that will be evaluated are listed below, followed by the descriptions of the derivations of selected endpoints.

9.4.1 Efficacy Endpoints

Primary Endpoints

- **ORR:** defined as the proportion of participants with a confirmed (≥ 4 weeks after initial response) CR or PR per RECIST 1.1 or RANO for HGG as assessed by investigator, at Week 16.

Secondary Endpoints

- **ORR.**
- **BOR:** defined as the participant's best confirmed response (CR or PR) over the treatment period.
- **DOR:** defined as the time from the date of the first documented CR or PR to the date of the disease progression objectively documented or death (whichever occurs first).
- **DCR:** defined as the percentage of participants who have a BOR of CR, PR, or SD. To be assigned a best overall response of SD, the time from the first administration of study drug until the date of documented SD should be ≥ 7 weeks.
- **CBR:** defined as the percentage of participants who have a BOR of CR, PR, or durable SD (SD duration ≥ 23 weeks since the first dose of the study treatment).
- **PFS:** defined as the time from the date of the first administration of study drug until the date of first documentation of PD per RECIST 1.1 or RANO for HGG or death (whichever occurs first).

Tertiary/Exploratory Endpoints

- **OS:** defined as the time from the date of the first administration of study drug until the date of death from any cause.

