1 PROTOCOL SUMMARY

1.1 Synopsis

Protocol Title: An Open-Label, Multicenter Phase 2 Basket Study to Evaluate the Antitumor Activity and Safety of Lenvatinib in Children, Adolescents, and Young Adults with Relapsed or Refractory Solid Malignancies

Short Title: Lenvatinib for Pediatric Patients with Relapsed/Refractory Solid Tumors

Acronym: Protocol 013 (E7080-G000-231)

Hypotheses, Objectives, and Endpoints:

In children, adolescents, and young adults with relapsed or refractory solid malignancies treated with lenvatinib:

Primary Objectives	Primary Endpoints
- To determine the ORR at Week 16, by each tumor type, per RECIST 1.1 or RANO (for HGG only) as assessed by the investigator.	- Objective Response, defined as a confirmed (≥ 4 weeks after initial response) CR or PR.
Secondary Objectives	Secondary Endpoints
- To evaluate ORR, by each tumor type, per RECIST 1.1 or RANO (for HGG only) as assessed by the investigator.	- Objective Response, defined as a confirmed (≥ 4 weeks after initial response) CR or PR.
- To evaluate PFS per RECIST 1.1 or RANO (for HGG only), by each tumor type.	- PFS defined as the time from the date of the first administration of lenvatinib until the date of first documentation of PD or death (whichever occurs first).
- To evaluate the BOR, DOR, DCR, and CBR, by each tumor type.	- BOR defined as the participant's best confirmed response (CR or PR) over the treatment period. - DOR defined as the time from the date of the first documented CR or PR to the date first documentation of progressive disease or death (whichever occurs first). - Disease control defined as a BOR of CR or PR, or SD. To be assigned a BOR of SD, the time from the first administration of study drug until the date of documented SD should be ≥ 7 weeks. - Clinical benefit defined as a BOR of CR or PR, or durable SD (SD duration ≥ 23 weeks since the first dose of the study treatment).

- To evaluate the safety of lenvatinib.	- AEs, SAEs, clinical laboratory values, vital signs, 12-lead ECGs, urine dipstick, Lansky play scores or Karnofsky performance status scores, physical examination findings, dental examination findings, height, and closure of proximal tibial plates.
- To assess the palatability and acceptability of the suspension formulation of lenvatinib.	- Palatability questionnaire using a facial hedonic scale.
- To characterize the PK of lenvatinib.	- Assessment of population-based PK parameters of lenvatinib.

Overall Design:

Study Phase	Phase 2

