9.6 Statistical Methods

9.6.1 Statistical Methods for Efficacy Analyses

This section describes the statistical methods that address the primary and secondary efficacy objectives. Methods related to exploratory objectives will be described in the sSAP.

Antitumor activity data will be analyzed by each tumor type. The data cutoff for the primary study analysis for a given tumor type will be determined by the study team, based on the review of data at each interim analysis and predetermined futility guidance.

Only those participants who have measurable disease present at baseline and have their disease re-evaluated at postbaseline visits will be considered evaluable for ORR. These participants will have their response classified according to RECIST 1.1 or RANO for participants with HGG.

Primary Efficacy Analysis

ORR: Objective responses will count only confirmed CR and PR at Week 16. Estimated ORR and its exact 95% CI using the method of Clopper and Pearson will be presented.

Secondary Efficacy Analyses

The BOR will be provided with the descriptive statistics. The ORR, DCR, and CBR will be provided with exact 95% CIs using the method of Clopper and Pearson, and the DOR will be analyzed for responders using Kaplan-Meier approach.

The secondary endpoint of PFS will be analyzed using Kaplan-Meier product-limit estimates. Median PFS and the cumulative probability of PFS at 4, 6, 12, and 24 months will be presented with 2-sided, 95% CIs when an adequate number of at-risk participants at those time points warrant the estimate. The cumulative PFS probabilities will be plotted over time as appropriate.

A summary of the primary analysis strategy for the key efficacy endpoints is provided in [Table 5](#).

Table 5 Table Analysis Strategy for Key Efficacy Variables

Endpoint/Variable	Statistical Method	Analysis Population	Missing Data Approach
Primary Analyses – Within tumor type			
ORR (RECIST 1.1 or RANO for HGG) at Week 16	Summary statistics using Clopper and Pearson method	EAS	Participants in EAS with missing data are considered nonresponders.
Secondary Analyses – Within tumor type			
ORR	Summary statistics using Clopper and Pearson method	EAS	Participants in EAS with missing data are considered nonresponders.
BOR	Summary statistics using Clopper and Pearson method	EAS	Missing observation in EAS population are counted as nonresponders.

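### BOR is limited to confirmed CR or PR during treatment, which contradicts DCR and CBR and does not match the window of ORR

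*Combined protocol and SAP*

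**What the plan says.** Section 9.4.1 defines BOR as the participant's "best confirmed response (CR or PR) over the treatment period". The endpoint tables in Sections 1.1 and 3 carry the same definition, and Section 4.2.1.1 repeats the treatment-period window.

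The next endpoints in Section 9.4.1 use BOR differently. DCR is the percentage of participants "who have a BOR of CR, PR, or SD", followed by a condition on SD that begins "To be assigned a best overall response of SD, the time from the first administration of study drug" and sets a minimum of 7 weeks. CBR is the percentage "who have a BOR of CR, PR, or durable SD", where durable means at least 23 weeks from first dose.

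ORR is not defined through BOR. The secondary objective in Section 1.1 is "To evaluate ORR, by each tumor type, per RECIST 1.1 or RANO (for HGG only) as assessed by the investigator"; its endpoint is a confirmed CR or PR, with no time window. For the primary, Section 9.6.1 says "Objective responses will count only confirmed CR and PR at Week 16". That is a calendar limit, not a treatment limit.

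Imaging does not end with treatment. Section 8.11.5.2 says: "Participants who discontinue lenvatinib for a reason other than disease progression and/or initiation of new anticancer therapy will move into the Efficacy Follow-up" phase. Sections 4.1 and 8.2.1.3 also provide for continued scans. Section 8.2.1.2 places the confirming scan at least 4 weeks after the first sign of response. Table 5 uses the evaluable analysis set for ORR, DCR and CBR alike. Appendix 8 refers the reader to the SAP for deriving best overall response from the visit responses, but the unredacted text of Section 9 gives no derivation.

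**The concern.** There are two faults in one definition.

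- **Category.** A BOR that can only be CR or PR cannot supply the SD that DCR and CBR need.
- **Window.** BOR stops with treatment and ORR does not. A response that appears shortly before lenvatinib is stopped for a reason other than progression may be confirmed only on a follow-up scan. The same participant can then be a responder for ORR and a failure for CBR.

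CBR includes every CR and PR by construction, so readers expect it to be at least as large as ORR. In cohorts of 9 to 17, one participant classified differently in two tables is visible. An analyst would probably repair the category fault without being asked. The window is a stated rule and may well be programmed as it stands.

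**Working it through.** **Inputs.** The definitions are from Sections 1.1, 3 and 9.4.1. Scans are at Weeks 8, 16 and 24 (±7 days), with confirmation at least 4 weeks later (Section 8.2.1.2). Post-treatment imaging is from Sections 4.1, 8.2.1.3 and 8.11.5.2. The denominators are 9 (first stage) and 17 (cap), from Section 4.1. The plan states no figure on this point, so there is none to reproduce. As a check on the interval method, Clopper-Pearson for 2/30 gives 6.7% (0.8, 22.1), which matches the osteosarcoma result in Section 2.2.1.2.

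**One hypothetical participant.** PR at Week 8, lenvatinib stopped at Week 10 without PD, PR confirmed at Week 16, PD at Week 24. This participant is a responder for the Week 16 ORR and for the secondary ORR. The other two rates depend on how BOR is read:

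| Reading of BOR | DCR | CBR |
|---|---|---|
| 1. Literal: CR or PR only, confirmed on treatment | no | no |
| 2. SD added, on-treatment scans only | yes (SD at Week 8, at least 7 weeks) | no (last on-treatment scan at Week 8, below 23 weeks) |
| 3. SD added, same window as ORR | yes | yes |

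Reading 2 needs two rules that the plan does not state: the confirming scan must fall on treatment, and an unconfirmed PR is recoded as SD.

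**Cohort level, reading 2.** Let a = responders confirmed on treatment, b = responders confirmed only off treatment and not credited with durable SD, c = responders confirmed only off treatment but credited with durable SD, and d = nonresponders with durable SD.

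- ORR = (a + b + c)/n
- CBR under reading 2 = (a + c + d)/n
- CBR with a common window = (a + b + c + d)/n

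The loss in CBR against the common window is b/n. With b = 1 it is 1/9 = 11.1 points or 1/17 = 5.9 points. CBR is below ORR only when b > d.

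**Numbers with a = 1, b = 1, c = 0, d = 0 (exact 95% CI).**

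- n = 9: ORR 2/9 = 22.2% (2.8, 60.0); CBR 1/9 = 11.1% (0.3, 48.2).
- n = 17: ORR 2/17 = 11.8% (1.5, 36.4); CBR 1/17 = 5.9% (0.1, 28.7).

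**Sensitivity to d, with n = 9, a = 2, b = 1, c = 0.** ORR is 3/9 throughout. CBR is 2/9 for d = 0, 3/9 for d = 1 and 4/9 for d = 2. The totals invert only in the first case.

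**Reading 1.** No SD can ever be counted, so DCR and CBR both collapse to the on-treatment response rate. A single response confirmed off treatment is then enough to put both below ORR.

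**Common window (reading 3).** Every ORR responder has a BOR of CR or PR, and SD of at least 23 weeks is also SD of at least 7 weeks. Hence secondary ORR ≤ CBR ≤ DCR always. In the n = 9 example, CBR rises from 1/9 to 2/9 and equals ORR.

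**The case against.** Much of the case on the other side stands.

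- **SD was plainly meant.** The 7-week clause treats SD as an assignable BOR, and Sections 2.2.1.2 and 4.3 report SD as a BOR for the earlier pediatric study. The category fault is therefore a drafting error that is unlikely to survive into the tables.
- **The window conflict rests on readings.** The wording does not say that the confirming scan must be on treatment; a PR first seen on treatment and confirmed later could be held to fit. Secondary ORR might also be taken as the proportion with a BOR of CR or PR, in which case CBR could not fall below it. Both are possible, but the plan states neither.
- **Durable SD may rescue the participant.** The 23-week clause has no on-treatment limit of its own, and the end point of SD duration is not defined. If it runs to progression, the example participant, with PD at Week 24, counts for CBR.
- **Few participants are exposed.** The only single-agent response rate reported as a percentage is 2/30, in osteosarcoma, which this trial excludes. At that rate the expected responders of any kind are 9 × 2/30 = 0.6 and 17 × 2/30 = 1.1 per cohort, and those confirmed only off treatment are a subset. EWS and HGG were not expanded (Sections 1.1 and 4.4), so among the three target cohorts only RMS can reach 17.

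A reader might infer that cohort CBR will be reported below ORR. The documents do not support that: under reading 2 it happens only if the affected responders outnumber nonresponders with durable SD. Nor are these responses lost to the trial, because ORR still counts them.

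**Conclusion.** The definition of BOR is wrong as written, because it excludes the SD category that DCR and CBR require, and nothing in the documents aligns its treatment-period window with that of ORR. If confirmation is required on treatment, each response confirmed only after the stop, without credited durable SD, lowers CBR by 11.1 points at n = 9 or 5.9 points at n = 17 against a common-window CBR. The number of such participants is an assumption, since the documents give no rate. With 0 to 1 per cohort, the loss ranges from 0 to 11.1 points at n = 9 and from 0 to 5.9 points at n = 17. Once SD is admitted, DCR would normally be unaffected.

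It would be tempting to conclude that the main result is at risk. It is not: the Week 16 ORR and the rule to stop after no responses in 9 do not use BOR. This is a minor correction to secondary, descriptive endpoints, and one that should be uncontroversial.

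**What to change.** Replace the BOR definition in Sections 1.1, 3 and 9.4.1, and align the mention in Section 4.2.1.1. BOR should be the best of confirmed CR, confirmed PR, SD (at least 7 weeks from first dose), PD or NE. It should use all assessments from first dose until PD or the start of new anticancer therapy, whichever is first, including scans after lenvatinib is stopped. Derive secondary ORR, DCR and CBR from this one variable, and leave the primary ORR at its Week 16 cut.

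In the same edit, state how an unconfirmed CR or PR is classified and at what date SD duration ends, because the 23-week criterion depends on both.

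The cost is one definition in a few places. No new data, visits or scans are needed. It should be settled before database lock.

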9.4.2 Safety Endpoints

Safety and tolerability will be assessed by clinical review of all relevant parameters, including AEs, SAEs, clinical laboratory values, vital signs, 12-lead ECGs, urine dipstick, Lansky play scores or KPS scores, physical examination findings, dental examination findings, height, and closure of proximal tibial plates.

